11.1 Ethical considerations and EC approval

The study will be conducted in accordance with all appropriate regulatory requirements and under an approved protocol. The study will be conducted in accordance with current ICH GCP, all applicable patient privacy requirements and the ethical principles outlined in the Declaration of Helsinki.

12 Financing, Indemnity and Insurance

The Sponsor will have a commercial contract in place with the CRO and the hospitals/universities will be responsible for any payments to patients for payment of travel and other expenses reimbursable by the Sponsor on delivery of receipts.

The Sponsor has a clinical trials insurance policy in place. A copy of the policy/certificate of insurance will be supplied separately. Provision is made for (1) The indemnity or compensation in the event of injury or death attributable to the clinical trial and (2) Insurance or indemnity to cover the liability of the Investigator or Sponsor.

Akari Therapeutics Plc will indemnify the Investigators from all or any claims arising out of this study except for their negligence or malpractice and providing that the study is conducted according to the standards established by the protocol.

In the event that it can be demonstrated that a patient suffers any significant deterioration in health or well-being or any harmful susceptibility or toxicity, as a direct result of their participation in this study, then Akari Therapeutics Plc will agree to abide by the current Association of the British Pharmaceutical Industry (ABPI) Guidelines with regard to compensation payable to the patient residing in the UK. The amount of compensation will be calculated by reference to the level of damages commonly awarded according to local law for similar injuries occurring in patients residing outside the UK.

13 Publication Policy

The key design elements of this protocol will be posted in a publicly accessible database.

The CRO has no independent publication rights.

Akari Therapeutics Plc actively encourages publication of clinical trial data in reputable peer reviewed journals. Authorship will be discussed and agreed in advance. If the Investigator drafts a publication, he/she agrees to send it to Akari Therapeutics for review and comment before its submission to the journal. In cases where Akari Therapeutics Plc considers that the proposed publication contains information which should be protected as valuable confidential information or is out of compliance with applicable laws and regulations, Akari Therapeutics Plc reserves the right to delay submission to the journal, until the required deletion or amendment of the confidential information from the proposed publication has been performed.

14 Study Record Retention

The Investigators shall ensure that the documents contained in the Investigator Site File are retained for 15 years after the conclusion of the trial. The Sponsor shall ensure that the documents contained in the Trial Master File are retained for 25 years after the conclusion of the trial. The Sponsor and Investigators will ensure that during this period the files are complete, legible and readily available to the licensing authority on request.

All data derived from the study will remain the property of Akari Therapeutics Plc.

All correspondence (e.g. with the Sponsor, or designee, Ethics Committee) relating to this study should be kept in the appropriate files. Records of patient's source documents, eCRF's, IMP inventory pertaining to the study must be kept on file.

If the Investigator moves, withdraws from the study or retires, the responsibility for maintaining the records may be transferred to another person who will accept responsibility. Notice of transfer must be made to and agreed by the Sponsor.

14.1 Clinical study report (CSR)

The results of this clinical study must be summarised by the Sponsor (or designee) and a final audited report must be retained on file. This report will include discussions on the study objectives, methodology, findings and conclusions. The Principal Investigator(s) will be asked to review and comment on the draft report and the Chief Investigator will be required to sign the final version. All Investigators will be provided with a final copy of the Clinical study report. The report must be archived with all other study documents. An interim CSR may also be required to support authorisation applications.

Appendix 1:

[Redacted]

[Redacted]	[Redacted]	[Redacted]	[Redacted]
[Redacted]	[Redacted]	[Redacted]	[Redacted]
[Redacted]	[Redacted]	[Redacted]	[Redacted]
[Redacted]	[Redacted]	[Redacted]	[Redacted]
[Redacted]	[Redacted]	[Redacted]	[Redacted]
[Redacted]	[Redacted]	[Redacted]	[Redacted]
[Redacted]	[Redacted]	[Redacted]	[Redacted]

[REDACTED]	[REDACTED]	[REDACTED]	[REDACTED]
[REDACTED]	[REDACTED]	[REDACTED]	[REDACTED]
[REDACTED]	[REDACTED]	[REDACTED]	[REDACTED]
[REDACTED]	[REDACTED]	[REDACTED]	[REDACTED]
[REDACTED]	[REDACTED]	[REDACTED]	[REDACTED]

Appendix 2:

[Redacted text block]

[REDACTED]

[REDACTED]

[REDACTED]

[REDACTED]

[REDACTED]

[REDACTED]

[REDACTED]

- [REDACTED] [REDACTED]
[REDACTED]
[REDACTED]
[REDACTED]
[REDACTED]
[REDACTED]

- [REDACTED] [REDACTED]
[REDACTED]
[REDACTED]
[REDACTED]

- [REDACTED] [REDACTED]
[REDACTED]
[REDACTED]
[REDACTED]
[REDACTED]
[REDACTED]

- [REDACTED] [REDACTED]
[REDACTED]
[REDACTED]
[REDACTED]
[REDACTED]
[REDACTED]

- [REDACTED] [REDACTED]
[REDACTED]
[REDACTED]
[REDACTED]
[REDACTED]
[REDACTED]

- [REDACTED] [REDACTED]
[REDACTED]
[REDACTED]
[REDACTED]
[REDACTED]
[REDACTED]

- [REDACTED] [REDACTED]
[REDACTED]
[REDACTED]
[REDACTED]

- [REDACTED] [REDACTED]
[REDACTED]
[REDACTED]

[REDACTED]

[REDACTED]

[REDACTED]

[REDACTED]

[REDACTED]

[Redacted]

[Redacted]

- [Redacted]

[Redacted]

- [Redacted]

- Change [REDACTED]

[REDACTED]			
[REDACTED]	[REDACTED]		
[REDACTED]	[REDACTED]		
[REDACTED]	[REDACTED]		
[REDACTED]			
[REDACTED]		[REDACTED]	
[REDACTED]	[REDACTED]	[REDACTED]	[REDACTED]
[REDACTED]	[REDACTED]	[REDACTED]	[REDACTED]
[REDACTED]	[REDACTED]	[REDACTED]	[REDACTED]
[REDACTED]	[REDACTED]	[REDACTED]	[REDACTED]
[REDACTED]	[REDACTED]	[REDACTED]	[REDACTED]
[REDACTED]	[REDACTED]	[REDACTED]	[REDACTED]
[REDACTED]	[REDACTED]	[REDACTED]	[REDACTED]
[REDACTED]	[REDACTED]	[REDACTED]	
[REDACTED]	[REDACTED]	[REDACTED]	
[REDACTED]	[REDACTED]	[REDACTED]	

[REDACTED]

[REDACTED]	
[REDACTED]	[REDACTED]
[REDACTED]	[REDACTED]
[REDACTED]	[REDACTED]
[REDACTED]	

[REDACTED]		[REDACTED]	
[REDACTED]	[REDACTED]	[REDACTED]	[REDACTED]
[REDACTED]	[REDACTED]	[REDACTED]	
[REDACTED]	[REDACTED]	[REDACTED]	[REDACTED]

[REDACTED]

Previous text:

[REDACTED]

[REDACTED]

[REDACTED]	[REDACTED]	[REDACTED]	[REDACTED]
[REDACTED]	[REDACTED]	[REDACTED]	[REDACTED]
[REDACTED]	[REDACTED]	[REDACTED]	[REDACTED]
[REDACTED]	[REDACTED]	[REDACTED]	[REDACTED]
[REDACTED]	[REDACTED]	[REDACTED]	[REDACTED]
[REDACTED]	[REDACTED]	[REDACTED]	[REDACTED]
[REDACTED]	[REDACTED]	[REDACTED]	[REDACTED]

[REDACTED]

[REDACTED]	[REDACTED]	[REDACTED]	[REDACTED]
[REDACTED]	[REDACTED]	[REDACTED]	[REDACTED]
[REDACTED]	[REDACTED]	[REDACTED]	[REDACTED]
[REDACTED]	[REDACTED]	[REDACTED]	[REDACTED]

[REDACTED]

[REDACTED]

- [REDACTED]

- [REDACTED]

[REDACTED]

[REDACTED]

[REDACTED]

[REDACTED]

[REDACTED]

[Redacted text block]

[Large redacted text block]

[Redacted text block]

[Redacted text block]

[Redacted text block]

[figure not shown]
[REDACTED]

[REDACTED]

[REDACTED]

[REDACTED]

[REDACTED]	[REDACTED]	[REDACTED]					
		[REDACTED]	[REDACTED]	[REDACTED]	[REDACTED]	[REDACTED]	[REDACTED]
[REDACTED]		[REDACTED]	[REDACTED]	[REDACTED]	[REDACTED]	[REDACTED]	[REDACTED]
[REDACTED]							
[REDACTED]							
[REDACTED]							
[REDACTED]							

[REDACTED]

[REDACTED]

[REDACTED]

[REDACTED]

[REDACTED]

- [REDACTED]

[REDACTED]

[REDACTED]	[REDACTED]	[REDACTED]	[REDACTED]
[REDACTED]	[REDACTED]	[REDACTED]	[REDACTED]
[REDACTED]	[REDACTED]	[REDACTED]	[REDACTED]
[REDACTED]	[REDACTED]	[REDACTED]	[REDACTED]
[REDACTED]	[REDACTED]	[REDACTED]	[REDACTED]

[REDACTED]

- [REDACTED]
- [REDACTED]
- [REDACTED]

[REDACTED]

- [REDACTED] [REDACTED]
[REDACTED]
[REDACTED]
[REDACTED]
[REDACTED]
[REDACTED]

[REDACTED]
[REDACTED]
[REDACTED]
[REDACTED]
[REDACTED]

[REDACTED]
[REDACTED]
[REDACTED]
[REDACTED]
[REDACTED]

[REDACTED]
[REDACTED]
[REDACTED]

- [REDACTED] [REDACTED]
[REDACTED]
[REDACTED]
[REDACTED]
[REDACTED]
[REDACTED]
[REDACTED]
[REDACTED]

- [REDACTED] [REDACTED]
[REDACTED]
[REDACTED]
[REDACTED]

- [REDACTED]
■ [REDACTED]
■ [REDACTED]
[REDACTED]
[REDACTED]

- [REDACTED]

[REDACTED]

[REDACTED]

[REDACTED]

[REDACTED]

[REDACTED]

[REDACTED]

[REDACTED]

- [REDACTED]
- [REDACTED]
- [REDACTED]
- [REDACTED]

[REDACTED]

[REDACTED]

[REDACTED]	[REDACTED]

[REDACTED]

[REDACTED]

[REDACTED]

[REDACTED]

[REDACTED]

[REDACTED]

[REDACTED]

[REDACTED]

- [REDACTED]

[REDACTED]

[REDACTED]

[REDACTED]

[REDACTED]

[REDACTED]

- [REDACTED]
- [REDACTED]
- [REDACTED]
- [REDACTED]
- [REDACTED]
- [REDACTED]
- [REDACTED]
- [REDACTED]
- [REDACTED]
- [REDACTED]

[REDACTED]

[REDACTED]

- [REDACTED]
- [REDACTED]
- [REDACTED]
- [REDACTED]
- [REDACTED]
- [REDACTED]

- [REDACTED]

[REDACTED]

[REDACTED]

[REDACTED]

[REDACTED]

[REDACTED]

[REDACTED]

[REDACTED]

- [REDACTED]
- [REDACTED]
- [REDACTED]
- [REDACTED]
- [REDACTED]
- [REDACTED]
- [REDACTED]
- [REDACTED]
- [REDACTED]
- [REDACTED]
- [REDACTED]
- [REDACTED]
- [REDACTED]
- [REDACTED]
- [REDACTED]
- [REDACTED]

[REDACTED]

[REDACTED]

[REDACTED]

[REDACTED]

- [REDACTED]

- [REDACTED]
- [REDACTED]

[REDACTED]

[REDACTED]

- [REDACTED]

[REDACTED]

[REDACTED]

[REDACTED]

[REDACTED]

[REDACTED]

[REDACTED]

- [REDACTED]

- [REDACTED]

[REDACTED]

- [REDACTED]

- [REDACTED]

- [REDACTED]

[REDACTED]

[REDACTED]	[REDACTED]	[REDACTED]	[REDACTED]	[REDACTED]
[REDACTED]	[REDACTED]	[REDACTED]	[REDACTED]	[REDACTED]
[REDACTED]	[REDACTED]	[REDACTED]	[REDACTED]	[REDACTED]
[REDACTED]	[REDACTED]	[REDACTED]	[REDACTED]	[REDACTED]
[REDACTED]	[REDACTED]	[REDACTED]	[REDACTED]	[REDACTED]
[REDACTED]	[REDACTED]	[REDACTED]	[REDACTED]	[REDACTED]

[REDACTED]

[REDACTED]	[REDACTED]	[REDACTED]	[REDACTED]
[REDACTED]	[REDACTED]	[REDACTED]	[REDACTED]

[REDACTED]	[REDACTED]	[REDACTED]	[REDACTED]
------------	------------	------------	------------

[REDACTED]

[REDACTED]

[REDACTED]

- [REDACTED]
- [REDACTED]
- [REDACTED]
- [REDACTED]

[REDACTED]

[REDACTED]

[REDACTED]

[REDACTED]

[REDACTED]

- [REDACTED]
- [REDACTED]
- [REDACTED]

[REDACTED]

[Redacted text block]

- [Redacted list item]
- [Redacted list item]
- [Redacted list item]

- [Redacted list item]

- [Redacted list item]

[Redacted text block]

[Redacted text block]

[REDACTED]

[REDACTED]

[REDACTED]

[REDACTED]

[REDACTED]

[REDACTED]

[REDACTED]

- | [REDACTED]
- | [REDACTED]
- | [REDACTED]
- | [REDACTED]
- | [REDACTED]
- | [REDACTED]
- | [REDACTED]

[REDACTED]

[REDACTED]

[REDACTED]

[REDACTED]

- | [REDACTED]
- | [REDACTED]
- | [REDACTED]
- | [REDACTED]
- | [REDACTED]

[Redacted text block]

[Redacted]	[Redacted]
[Redacted]	[Redacted]
[Redacted]	[Redacted]
[Redacted]	[Redacted]

[Redacted text block]

[REDACTED]	[REDACTED]	[REDACTED]	[REDACTED]	[REDACTED]
[REDACTED]	[REDACTED]	[REDACTED]	[REDACTED]	[REDACTED]
[REDACTED]	[REDACTED]	[REDACTED]	[REDACTED]	[REDACTED]
[REDACTED]	[REDACTED]	[REDACTED]	[REDACTED]	[REDACTED]

[REDACTED]

[REDACTED] ts

- [REDACTED]

- [REDACTED]
[REDACTED]
[REDACTED]
[REDACTED]
[REDACTED]
- [REDACTED]
[REDACTED]
[REDACTED]
[REDACTED]
[REDACTED]
- [REDACTED]
[REDACTED]
[REDACTED]
[REDACTED]
[REDACTED]

This SAP only describes the analyses that will be performed for PNH patients given that the aHUS trial has been terminated due to inability to recruit. Therefore as no aHUS patients will enter AK581, all references to objectives and analyses related to aHUS patients have been removed from this SAP.

2 Study Objectives and Study Design

The objective of the trial is to provide a database of information regarding long-term administration of rVA576 (Coversin) to show that it remains safe for long periods and is acceptable to patients and show that the effect observed in the previous clinical trial is maintained. It also provides the opportunity to adjust an individual patient's dose or dose frequency should it be considered desirable. All patients enrolled into the CONSERVE study will have transitioned from a parent clinical trial.

2.1 Study Objectives

The specific objectives of the study are:

- To observe the long term safety and efficacy of rVA576 (Coversin)
- To assess the long term patient acceptability of rVA576 (Coversin) using the EORTC QLQ-C30 (for some PNH only), EQ-5D-5L & FACIT-F instruments and the Sponsor non validated questionnaire.
- To observe the changes, if any, in the production of anti-drug antibodies (ADA) and whether such antibodies are, or become, neutralising.

2.2 Study Design

The trial is an open-label, non-comparative study in up to approximately 50 patients, 18 years and above with either PNH or aHUS who have participated in another rVA576 (Coversin) and who wish to remain on the study.

The study population will consist of patients with diseases requiring complement inhibition who have previously taken part in Akari clinical trials and who wish to

continue to receive rVA576 (Coversin) after their active participation in the previous trial has completed and patients treated under compassionate use or named patient arrangements who wish to continue on rVA576 (Coversin) therapy.

The study visit schedule and procedures intended to be performed at each visit are displayed in the study protocol Tables 8 and 9.

2.3 Study Data

All patients enrolled into the CONSERVE study will have transitioned from a parent clinical trial and all will have been previously treated with rVA576.

Parent trial data used to assess patient safety and eligibility for enrollment will be entered into the AK581 database. Where applicable, assessment data collected at the subject's parent trial end of study visit will be captured. Coversin dosing history, parent trial ECG and LDH results, and plasma (blood) transfusion/dialysis history will be available in the AK581 subject casebooks.

Where applicable and where possible, parent trial locked databases will be used and pooled with the AK581 database:

- Raw data from AK578 CONSENT
- Study Data Tabulation Model (SDTM) and/or Analysis Data Model (ADaM) datasets from AK579 COBALT
- SDTM and/or ADaM datasets from AK580 CAPSTONE

See section 3.1, for the definitions of baseline (study entry) and parent trial baseline.

2.4 Study Endpoints

2.4.1 Primary Endpoint

Long term safety of rVA576 (Coversin) therapy as assessed by AEs, serious adverse events (SAEs), vital signs, results of standard laboratory tests (clinical chemistry, haematology and urinalysis), and results of electrocardiograms (ECGs).

2.4.2 Secondary Endpoints

1. Proportion of subjects with thrombotic and haemolytic event-free status during each 3 month time period since the start of the study.
2. Time to thrombotic or haemolytic event since the start of the study.
3. Proportion of subjects who require PRBC transfusion during each 3-month period since the start of the study and over the entire period of the study, with analysis of i) subjects who were transfusion-dependent when they started receiving rVA576 (Coversin), ii) subjects who were transfusion-independent when they started receiving rVA576 (Coversin), and iii) all subjects, and further stratification of these proportions by a) patients who were complement inhibitor-naïve prior to treatment with rVA576 (Coversin), and b) patients who received treatment with another complement inhibitor before switching to rVA576 (Coversin).
4. Time to first transfusion since joining the study.
5. Proportion of subjects with no adverse change in overall scores of Quality of Life using the EORTC QLQ-C30, the EQ-5D-5L and FACIT-F instruments at each 3-month time period since the start of the study.
6. Proportion of subjects with serum Lactate Dehydrogenase (LDH) <1.8, >1.8 to 2.4, >2.4 to 3, and >3 times the upper limit of normal (ULN) at each 3-month time period since the start of the study.
7. Proportion of subjects with median serum Lactate Dehydrogenase (LDH) <1.8, >1.8 to 2.4, >2.4 to 3, and >3 times the upper limit of normal (ULN) over the entire duration of the study.
8. Proportion of transfusion-independent subjects at each 3-month time point, with haemoglobin (g/L) above the baseline haemoglobin value they had at the start of the trial from which they entered CONSERVE. With baseline for CAPSTONE (AK580) defined as the haemoglobin value at which they received their qualifying transfusion (the set point) or for COBALT (AK579) and CONSENT (AK578) the haemoglobin value at which patients entered those trials. With separate analysis of subjects who were i) transfusion-independent prior to receiving rVA576 (Coversin) and remain transfusion-independent and ii) transfusion-dependent prior to receiving rVA576 (Coversin).
9. Proportion of transfusion-independent subjects over the entire duration of the study with mean haemoglobin (g/L) above the baseline haemoglobin value they had at the start of the trial from which they entered CONSERVE. With baseline haemoglobin defined as for the previous secondary endpoint (#8). With separate analysis of subjects who were i) transfusion-independent prior to receiving rVA576 (Coversin) and remain transfusion-independent and ii) transfusion-dependent prior to receiving rVA576 (Coversin).

10. Proportion of patients experiencing Major Adverse Vascular Events (MAVE) over the entire period of the study.
11. Time to first Major Adverse Vascular Event (MAVE) for each subject since joining the study.
12. Number of Major Adverse Vascular Events (MAVE) over the entire period of the study.

2.5 Additional Endpoints:

PK and PD parameters during treatment, to include terminal complement activity measured by CH50 ELISA, unbound nomacopan concentration measured by ELISA and total C5 concentration measured by ELISA.

3 Efficacy and Safety Variables

3.1 Baseline (study entry) and Parent trial Baseline

In order to describe changes over time, and compare values to the pre-Coversin dosing value (historical baseline), some parameters (LDH, CH50, quality of life scores, haemoglobin) may have both parent trial baseline values and CONSERVE baseline values used in analyses. To avoid any confusion the term “baseline” will always refer to CONSERVE baseline, while ‘Parent trial baseline’ will be used otherwise.

Baseline will therefore be defined as the last measurement prior to CONSERVE study entry.

Parent trial baseline will be defined as :

- Baseline for CAPSTONE (AK580) defined as the value at which they received their qualifying transfusion (the set point)
- Baseline for COBALT (AK579) or CONSENT (AK578) the value at which patients entered those trials.

3.2 Entry

Written informed consent will be obtained before any study procedures are performed. The following procedures will be performed exclusively at the Entry visit.

3.2.1 *Medical History*

A complete medical history will include an evaluation of the previous medical history from the previous rVA576 (Coversin) trial which will be transferred to the current database.

As all patients enrolled into the CONSERVE study will have transitioned from a parent clinical trial, a full new medical history and examination is not considered necessary unless there has been a lag time in entry into the long term study. The investigator responsible for the patient’s treatment will decide if there have been significant changes in the patient’s condition since being in the previous study to warrant an additional examination and new entries to the medical history page. If there has been development of a new medical condition (with diagnosis) in the previous study this will be considered as part of the patient’s medical history for this study.

All medical history data will be coded using the MedDRA dictionary version available at the time of the analysis.

3.2.2 *Demographics*

Demographic information (date/year of birth, age, sex, ethnicity, race and blood group) will be collected at study entry.

3.2.3 Eligibility

Evaluation of the study inclusion/exclusion criteria (see study AK581 trial Protocol sections 4.1 and 4.2) will be assessed at Entry.

3.2.4 Transfusions and Complement inhibitor history

Patients will be classified in subgroups as follows:

- i) Patients who were transfusion-dependent when they started receiving rVA576 (Coversin),
- ii) Patients who were transfusion-independent when they started receiving rVA576 (Coversin),

and further groupings will be performed as follows:

- a) Patients who were complement inhibitor-naïve prior to treatment with rVA576 (Coversin),
- b) Patients who received treatment with another complement inhibitor before of the switching to rVA576 (Coversin).

3.3 Efficacy Measurements and Variables

3.3.1 Blood transfusions

Details of blood transfusions administered during the study will be captured at all visits. Infusion type (PRBC or platelet), date, volume, reason and whether the transfusion was used as a method of PNH treatment will be recorded.

Patients who were transfusion-independent when they started receiving rVA576 (Coversin) and remain transfusion-independent will be identified.

3.3.2 Serum Lactate dehydrogenase (LDH)

Lactate dehydrogenase (LDH) values will be obtained as per the schedule of events. Changes and percent changes from the Parent trial baseline to each assessment of this study will be derived.

To permit the comparison of LDH values from different local laboratories, the ratio of the recorded LDH value to the local laboratory upper limit of normal (ULN) will be derived. Values below the ULN will provide a ratio of less than one; values above the ULN will provide a ratio of greater than one.

Indicators will be derived for each patient at every visit, to identify whether the LDH value ≤ 1.8 , >1.8 to 2.4 , >2.4 to 3 , and >3 times the ULN. The median serum LDH will also be derived for each patient.

3.3.3 CH50 Levels

Blood samples for CH50 will be collected as per the schedule of events and analysed in the Central Laboratory. The Central Laboratory considers values less than 10 CH50 U Eq/mL as completely inhibited. In previous trials (AK577, AK578 and AK579) with rVA576 (Coversin) the lower limit of quantification (LLOQ) of the CH50 was 8 CH50 EU/mL. The LLOQ has increased because the assay is now being performed using an automated system

for the ELISA. Results recorded as below the LLOQ will be imputed using half of the lower limit of quantification that applies to the sample for the purpose of calculating change from baseline, or percentage change from baseline, for summaries and figures.

The absolute change and percentage change from the parent trial Baseline to each subsequent assessment will be derived.

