5.5 Measurements conducted on blood draws

5.5.1 CH50 assay

It appears that in PNH and aHUS, close to 100% inhibition of CH50 activity is necessary for clinical control of the disease. Serum CH50 assay is currently the most sensitive and quickest means of detecting inadequate control during anti-complement therapy as other indicators, such as LDH lag 24 - 48 hours behind the change in CH50. In practice, the Quidel ELISA assay, which is used to measure complement activity in units of CH50 U Eq/mL has a lower limit of quantification (LLOQ) of 10 CH50 U Eq/mL with individual normal baseline values ranging from 58-156 CH50 U Eq/mL. Thus the assay is insensitive to differences in CH50 when there is <10 CH50 U Eq/mL residual complement activity. Therefore, for practical purposes, the Central Laboratory (which will conduct all CH50 assays during the trial) considers values less than 10 CH50 U Eq/mL as completely inhibited. In previous trials (AK577, AK578 and AK579) with rVA576 (Coversin) the LLOQ of the CH50 was 8 CH50 EU/mL. The LLOQ has increased because the assay is now being performed using an automated system for the ELISA.

CH50 samples will be collected as per Schedule of Events.

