3.4.10 Pharmacokinetic Coversin Levels

A blood sample for unbound rVA576 Coversin levels will be collected as per the schedule of events.

Unbound nomacopan, total C5 and serum LTB4 levels will be summarised overtime and spaghetti plot of concentrations through time will be produced.

Additional exploratory figures may be produced in order to investigate threshold levels that should be exceeded to ensure >90% inhibition of terminal complement activity. Additional PK analyses may be performed at a later stage and results reported separately from the main CSR.

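### Imputing below-LLOQ CH50 at half of each sample's own limit (4 on the older assay, 5 on the current one) gives false changes when the reference value is an AK578 or AK579 result

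*SAP*

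**What the plan says.** On imputation, SAP 3.3.3 states: "Results recorded as below the LLOQ will be imputed using half of the lower limit of quantification that applies to the sample". The rule serves changes, percentage changes, summaries and figures. SAP 4.5 repeats half of the LLOQ as the general laboratory rule, without addressing a limit that differs between samples.

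On the two limits, SAP 3.3.3 states: "In previous trials (AK577, AK578 and AK579) with rVA576 (Coversin) the lower limit of quantification (LLOQ) of the CH50 was 8 CH50 EU/mL". Protocol 5.5.1 says that the ELISA now "has a lower limit of quantification (LLOQ) of 10 CH50 U Eq/mL", and explains: "The LLOQ has increased because the assay is now being performed using an automated system for the ELISA".

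On the reference value, SAP 3.1 reserves the unqualified word baseline for CONSERVE, meaning the last measurement before entry. It allows CH50 to use the parent trial baseline as well. SAP 3.3.3 derives CH50 change from the parent trial baseline. SAP 4.11.4 and Tables 14.4.1.1 and 14.4.1.2 refer simply to baseline. SAP 2.3 pools parent-trial data where possible. Protocol 5.8 lets a parent-trial CH50 taken within 14 days serve at entry, provided that the reference laboratory is the same.

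On interpretation, Protocol 5.5.1 concedes that "the assay is insensitive to differences in CH50 when there is <10 CH50 U Eq/mL residual complement activity" and gives "individual normal baseline values ranging from 58-156 CH50 U Eq/mL". SAP 3.3.3 adds: "The Central Laboratory considers values less than 10 CH50 U Eq/mL as completely inhibited". SAP 3.4.10 allows optional exploratory figures on "threshold levels that should be exceeded to ensure >90% inhibition of terminal complement activity".

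**The concern.** Half-LLOQ substitution is harmless to change scores when every sample shares one limit, because two unquantifiable results then receive the same number. Here the limit can differ between a patient's reference value and later visits. Protocol 4.1 (criterion 3) makes CH50 evidence of sustained inhibition an entry condition, so a CONSERVE baseline at or below the limit is to be expected. The planned change and % activity tables could then report a loss or a gain of complement control that is only the change of assay. One stated aim of the study is to show that the parent-trial effect is maintained.

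A secondary issue is that the imputed 5 is a convention. If it is plotted as a measurement in the >90% inhibition figures, it implies more inhibition than a result below 10 demonstrates.

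**Working it through.** The plan gives no computed figure on this point, so there is none to reproduce.

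**Inputs.** LLOQ 8 for AK578 and AK579 (SAP 3.3.3); LLOQ 10 now (Protocol 5.5.1); normal individual values 58 to 156 (Protocol 5.5.1). The documents write the older unit as EU/mL and the current one as U Eq/mL; I take them as the same scale.

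**Formulas.** Imputed value = LLOQ/2. % activity = 100 × value/baseline. % inhibition = 100 − % activity. What a below-limit result supports: inhibition > 100 × (1 − limit/baseline).

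**1. Imputed values.** 8/2 = 4 and 10/2 = 5.

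**2. Older-assay reference, both results below their limits.** Change = 5 − 4 = +1 U. Percentage change = 1/4 = +25%. % activity = 5/4 = 125%. The reference is either a CONSERVE baseline taken from AK578 or AK579, or a parent baseline already suppressed, for example by another complement inhibitor.

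**3. Older-assay reference quantified at 8 to 9.9, true level unchanged, new result below 10.**
- From 8: (5 − 8)/8 = −37.5%
- From 9: (5 − 9)/9 = −44.4%
- From 9.9: (5 − 9.9)/9.9 = −49.5%

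So the artefact can run in either direction.

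**4. Quantified parent baseline.** No pair then has both values imputed. Substituting 5 rather than 4 moves % activity by 1/58 = 1.72 points, 1/100 = 1.00 point or 1/156 = 0.64 points.

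**5. Which denominator.** For a result below 10, the parent baselines in step 4 give 5/58 = 8.6% to 5/156 = 3.2% activity. A CONSERVE baseline of 4 gives 125%. The same sample can therefore read as 3.2% or 125%, depending on which SAP section the programmer follows.

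**6. What a below-limit result shows about inhibition.**

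| Parent baseline | Imputed 5 | Supported by <10 | Supported by <8 |
|---|---|---|---|
| 58 | 91.4% | >82.8% | >86.2% |
| 80 | 93.8% | >87.5% | >90% |
| 100 | 95.0% | >90% | >92.0% |
| 156 | 96.8% | >93.6% | >94.9% |

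A result <10 shows >90% inhibition only at parent baselines of 10/0.10 = 100 or more. For a result kept as <8, the cut-off is 8/0.10 = 80. Imputing 5 gives >90% at any baseline above 5/0.10 = 50, which covers the whole 58 to 156 range.

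**7. With one common limit of 10.** A pair below the limit becomes 5 and 5, a change of 0. An older 8 to 9.9 is also set to 5, so the false falls in step 3 become 0 too.

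**The case against.** Half-LLOQ is an ordinary convention, both limits are disclosed, SAP 4.5 keeps raw values in the listings, and all analyses are descriptive. CH50 appears only among the additional endpoints (SAP 2.5). Measured against a normal parent baseline, the reference that SAP 3.3.3 names, the 4-versus-5 step is under 2 points. All of this stands, and it limits the importance of the point. It does not remove the artefact, because SAP 4.11.4 read with 3.1 uses the CONSERVE baseline, and no sensitivity analysis for the change of limit is planned.

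Three stronger readings are tempting, and the documents do not support them.

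- A reader might infer a drift across AK581, or a false improvement from parent-trial visits to AK581 visits. With LLOQ 10 as the current limit, AK581 samples below it all receive 5, so there is at most one step at entry. A true 9 at parent baseline 58 would read 9/58 = 15.5% on the older assay and 5/58 = 8.6% now, but no listed table shows parent-trial on-treatment visits.
- A reader might infer that every patient is affected, whichever baseline is used. The +25% needs a below-limit older-assay reference. AK580 is not among the trials listed with LLOQ 8.
- A reader might infer that the plan formally classes every below-LLOQ sample as >90% inhibited. No endpoint, table or rule does so, and the SAP 3.4.10 figures are optional. Treating <10 as complete inhibition is the central laboratory's convention, not a product of the imputation. The cut-off of 100 also does not apply to LLOQ-8 results, for which it is 80. Against a below-limit CONSERVE baseline, the rule gives 100% or 125% activity, the opposite of >90% inhibition.

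**Conclusion.** The point holds in a limited form. The rule yields false CH50 changes for patients whose reference value comes from AK578 or AK579: +1 U, +25% or 125% activity if below both limits, and −37.5% to −49.5% if the older result was 8 to 9.9 and the new one is below 10. Where the reference is a quantified parent baseline in the 58 to 156 range, the 4-versus-5 effect is 0.6 to 1.7 points. The unresolved denominator of % activity can matter more to a reader of the tables than the imputed value itself.

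The >90% issue is secondary and arises only if the exploratory figures are produced. For parent baselines from 58 to just under 100, a result <10 does not by itself establish >90% inhibition, although the imputed value says so.

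This rests on three assumptions: post-entry AK581 samples are run at LLOQ 10, the two unit labels are equivalent, and the normal range of 58 to 156 describes these patients' parent baselines. The documents give neither the CH50 distribution of enrolled patients nor the number coming from AK578 or AK579, so the share affected is unknown. The primary and secondary endpoints do not use CH50 and are unaffected.

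**What to change.** In SAP 3.3.3 and 4.5, treat every CH50 result below 10 from either assay, including older values of 8 to 9.9, as <10. Give all of them one common imputed value (5, half of 10) in the change and ratio tables.

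Add the number and percentage of patients with CH50 <10 at each visit. This is the central laboratory's own definition of complete inhibition and needs no imputation.

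State in SAP 3.3.3 and 4.11.4 which baseline is the denominator of % activity, and label Tables 14.4.1.1 and 14.4.1.2 accordingly.

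If the >90% inhibition figures in SAP 3.4.10 are produced, show below-limit samples as bounds, inhibition > 1 − limit/parent baseline, and not at the imputed value. The common value belongs in the tables, not in these plots.

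The cost is some SAP wording and a few programming lines. The downside is that older-assay values of 8 to 9.9 are no longer used as numbers; they remain in the listings.
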